#### 4.3 Software

All report outputs will be produced using SAS® version 9.4 or a later version in a secure and validated environment.

#### 4.4 Study Patients

##### 4.4.1 Disposition of Patients

A clear accounting of the disposition of all patients who enter the study will be provided, from screening to study completion. Summaries will include:

- The number of patients randomized.
- Number and percentage of patients randomized by country
- The number and percentage of patients treated (with any amount of study drug).
- Number of patients in the analysis populations
- Number and percentage of patients who completed treatment
- Number and percentage of patients who were discharged from the hospital prior to Day 10.

- Number and percentage of patients withdrew early from treatment (including reasons for early withdrawal)
- Number and percentage of patients who withdrew early from the study (including reasons for early withdrawal)

By-patient listings of randomization details, visit dates, and withdrawal details (including reason for discontinuation and duration of treatment prior to discontinuation) will also be provided.

#### 4.4.2 Protocol Deviations

A protocol deviation is defined as any change, divergence, or departure from the study design or procedures of a study protocol likely to have an impact on the perceived efficacy and/or safety of study treatments.

Major protocol deviations are defined as those deviations from the protocol likely to have an impact on the perceived efficacy and/or safety of study treatments. The impact of major protocol deviations on the efficacy and/or safety results will be investigated by assessing the robustness of the study results and conclusions to the choice of analysis population (see [Section 4.5](#) for descriptions of analysis populations), both including and excluding data potentially affected by major protocol deviations.

A patient will be classified as having a protocol deviation if one incurs an event belonging to any one of the following categories: 1) violation of the inclusion/exclusion criteria (see Protocol Section 5.2 and 5.3); 2) taking prohibited medications or treatments; 3) treatment misallocation; 4) violation of discontinuation criteria; 5) error in procedure and tests; and 6) missed visits (including procedures and tests).

Major protocol deviations and any action to be taken regarding the exclusion of patients are defined in the study protocol deviation specifications. The final determination of major protocol deviations and the exclusion of patients from any of the analysis populations will be made prior to database lock.

A summary of the number and percentage of patients with a major protocol deviation by treatment arm as well as by type of deviation will be provided. Also, a by-patient listing of major protocol deviations will be provided.

#### 4.5 Analysis Sets

For purposes of analysis, the following analysis sets are defined:

- The intent-to-treat (ITT) population will include all randomized participants. The ITT participants will be analyzed according to randomized treatment, irrespective of the actual treatment received. Participants who withdraw from treatment early will be followed for the assessment of the Day 14 primary endpoint. All efficacy analyses will be performed using the ITT Population.

- The per-protocol (PP) population will include all participants in the ITT Population with no major protocol deviations that may significantly impact data integrity or patient safety. The PP Population will be used for supportive analyses of the efficacy measurements.
- The safety (SP) population will include all randomized participants who inhale any amount of study intervention or are randomized to the control arm. The SP will be analyzed according to the actual treatment received. The SP will be analyzed according to the actual treatment received. This set will be used for the safety analyses.

The efficacy summaries and analyses will be based on the ITT population. In the event that a patient is allocated the incorrect study treatment as per the study randomization list, patients will be summarized and analyzed 'as randomized' (i.e. by randomized treatment arm). In the event that a patient is stratified incorrectly, 'randomized stratum' will be used rather than 'actual stratum'. The PP Population will be used to demonstrate robustness of results for the primary efficacy endpoint

The safety summaries and analyses will be based on the SP population. In the event that a patient is allocated the incorrect study treatment as per the study randomization list, patients will be summarized and analyzed 'as treated' (i.e. by allocated treatment arm).

A by-patient listing of analysis population details will be provided. This listing will be presented by treatment arm and will include: center, patient identifier, inclusion/exclusion flag for each population, and reason for exclusion from each population.

#### 4.6 Demographic and Other Baseline Characteristics

Demographic and other baseline characteristics will be summarized by treatment group and overall using the ITT population. The summaries provided will include the following:

- Demographic variables:
  - Age (continuous and categorical (<65 years;  $\geq$ 65 years))
  - Sex
  - Race (American Indian or Alaska Native; Asian; Black or African American; Native Hawaiian or Other Pacific Islander; White; Other; Multiple)
  - Ethnicity (Hispanic or Latino, Not Hispanic or Latino)
  - Baseline Height (cm)
  - Baseline Weight (kg)
  - Baseline BMI ( $\text{kg}/\text{m}^2$ )
  - Pregnant (Yes, No)
  - Childbearing Potential (Yes, No)
- Baseline disease characteristics:
  - Randomization strata (country; comorbidity category)
  - SARS-CoV-2 Status (positive, negative, borderline, intermediate)
  - Mechanical ventilation (Yes, No)
  - Ventilation rate (liter per minute)

- Mode of Supplemental O2 Administration (Nasal Cannula, Mask)
- Respiratory rate (breaths per minute)
- Heart rate (Beats per minute)
- SpO2, FiO2, CCI
- NEWS Symptom Score
- WHO 7-point ordinal Scale
- Days since onset of symptoms
- Diastolic blood pressure (<=90 mmHg, >90 mmHg)
- Systolic blood pressure (<=140 mmHg, >140 mmHg)
- Temperature

Medical history will be reported by system organ class and preferred term as coded using the Medical Dictionary for Regulatory Activities (MedDRA) Version 23.0 or higher.

Age will be reported as calculated in the study database at day of informed consent. BMI will be calculated from baseline height and weight as weight (kg) / height (m^2).

By-patient listings of demographic data and other baseline characteristics will be provided.

#### 4.7 Prior, Concomitant Medication and Prohibited Medication

Prior and concomitant medications will be summarized by drug class and preferred medication name by treatment group and for both treatment groups combined (Total) using the ITT population. Prior and concomitant medications will be summarized separately, concomitant medications will also be summarized overall and by study period. WHO DDE March 2020 will be used to classify medications.

Medication start and stop dates will be compared to the date of first dose of study drug to allow medications to be classified as either Prior only, both Prior and Concomitant, or Concomitant only. Missing or partial start dates will be imputed as described in [Section 4.9.1.3](#). Medications starting after the completion/withdrawal date will be listed but will not be classified or summarized.

Medications that start and stop prior to the date of first dose of study drug will be classified as Prior only. If a medication starts before the date of first dose of study drug and stops on or after the date of first dose of study drug, then the medication will be classified as both Prior and Concomitant. Medications will be classified as Concomitant only if they have a start date on or after the date of first dose of study drug.

Rescue medication of a ready-to-use nebulization of a bronchodilator will be allowed on study. The number and percentages of the patients using such medications will be summarized by treatment groups, and the impact on efficacy and safety will be analyzed by subgroup analyses.

By-patient listings of prior, concomitant and rescue medications will be provided. Listings will also be provided for any concomitant procedures reported.

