## 1 INTRODUCTION

Coronavirus disease 2019 (COVID-19) is a respiratory illness caused by a novel coronavirus (SARS-CoV-2). COVID-19 was first described in Wuhan, China, in December 2019 and is now a global pandemic (Matos et al, 2020). Most of those affected have milder illness (80%), 15% will be severely ill (require oxygen) and 5% will require intensive care unit care (Novel Coronavirus Pneumonia Emergency Response Epidemiology Team, 2020). Of those who are critically ill, most require early intubation and mechanical ventilation.

A critical early component of innate host defense in the airway is the ability of respiratory epithelial cells to produce high levels of NO (Kao et al, 2001). NO functions as a signaling molecule in initiation of the inflammatory response to viruses, and also has direct antiviral effects (Folkerts et al, 1998).

RESP301 is a NO-generating liquid designed to release NO in situ in the upper airways and deep in the alveolar spaces. RESP301 is delivered via a handheld nebulizer and has specific advantages over inhaled NO gas in treating patients with COVID-19 during the current pandemic.

This is an open-label, randomized, multicenter, parallel group, concurrent, controlled study using a sequential adaptive design. Participants will be consented and randomized 2:1 to the Investigational arm or the Control arm. Participants randomized to the Investigational arm will receive inhaled RESP301 (6 mL) administered using a nebulizer 3 times a day (TID) for up to 10 days in addition to the standard of care (SOC) while participants in the Control arm will receive SOC alone.

The analyses described in this SAP are based upon the following study documents:

- Study Protocol, Version 4.0 (September 16, 2020 )
- electronic Case Report Form (eCRF), Version 3.0 (June 24, 2020)
- RESP301 DMC Charter

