### 3 INVESTIGATIONAL PLAN

### 3.1 Overall Study Design and Plan

This is an open-label, randomized, multicenter, parallel group, concurrent, controlled study using a sequential adaptive design to evaluate the efficacy and safety of RESP301 added to standard of care (SOC) in hospitalized patients with COVID-19 (WHO ordinal scale grade 3 & 4).

Central stratified randomization of 300 subjects to assign participants into one of the study treatment arms will occur as follows, RESP301+SOC or SOC (control), with a randomization ratio of 2:1 using an interactive voice response system (IVRS)/interactive web response system (IWRS). Participants will be stratified by country and presence of risk factors for severe outcomes of COVID-19, based on comorbidities and age as follows:

1. Age  $>65$  years
2. Ongoing or currently treated diabetes mellitus
3. Ongoing or currently treated hypertension
4. Ongoing or currently treated cardiovascular disease
5. Ongoing or currently treated chronic lung disease
6. Cancer history of less than 3 years, basal cell skin carcinoma excluded
7. Ongoing or currently treated chronic kidney disease

Participants will be stratified as no risk factor (none of the above criteria), one risk factor (one single of the above) or high-risk factor (2 or more of the above).

There are 3 phases in the overall study design: Screening Period, Intervention Period, Follow-up Period. Figure 1 displays the study schematic.

**Screening Period**– Patients will be screened up to 2 days prior to treatment administration. Upon signing informed consent, the patient enters the screening phase and is assessed for the inclusion/exclusion criteria. If all eligibility criteria are met, the patient moves into the intervention period.

[figure not shown]
**Intervention Period** – The intervention period starts on Treatment Initiation (Day 1). Patients will receive treatment three times a day up to Day 10. Patients may end treatment earlier than Day 10 if their symptoms subside following the criteria outline in the protocol section 4.1.

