#### 3.3.2 Safety Variables

- Clinical safety laboratory measurements
- Physical examinations
- Vital signs
- Concomitant medications
- Cumulative incidence of AEs and Severe AEs

CCI  
CCI  
CCI

CONFIDENTIAL

Project Document Version No. 2.0  
Project Document Effective Date: Date of last signature  
Page 11 of 31

- Incidence of participants unable to tolerate nebulization due to:
  - Reduction in SpO2 to < 90%, unless well clinically tolerated according to Investigator's opinion
  - Other clinical signs of intolerance according to Investigator's opinion
- Incidence of clinical bronchial hyper-responsiveness related to nebulization

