## 8. Ongoing or currently treated chronic kidney disease

Summaries of the primary and key secondary efficacy variables by treatment group and subgroups will be produced. No formal statistical analysis will be performed within subgroup.

With reviewing the results, the homogeneity of the treatment effect across subgroups may be investigated using graphical and analytical methods.

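### The SAP plans an efficacy analysis by rescue-bronchodilator use, a post-randomisation variable that treatment may influence, so arm contrasts within those subgroups are not randomised comparisons and can mislead in either direction

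*SAP*

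**What the plan says.** Section 4.7 of the current SAP (version 2.0) states: "Rescue medication of a ready-to-use nebulization of a bronchodilator will be allowed on study". It promises counts and percentages of users by treatment group and adds that "the impact on efficacy and safety will be analyzed by subgroup analyses". The sentence names efficacy as well as safety. It gives no method, estimand or caveat for a variable that arises during the trial.

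Four other places bear on it:

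- Section 1: "participants in the Control arm will receive SOC alone". No sham or placebo nebulisation is described for that arm.
- Section 3.1: "This is an open-label, randomized, multicenter, parallel group, concurrent, controlled study".
- Section 3.3.2 lists "Incidence of clinical bronchial hyper-responsiveness related to nebulization" as a safety variable, and also counts participants who cannot tolerate nebulisation.
- Section 4.9.1.6 lists the subgroups for the primary and key secondary endpoints: country, age over 65 and six comorbidity factors. All are baseline variables, and rescue use is not among them. The section then says: "No formal statistical analysis will be performed within subgroup".

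**The concern.** A subgroup comparison of the arms keeps the protection of randomisation only if treatment cannot influence subgroup membership. The factors in section 4.9.1.6 meet that condition. Rescue use need not, because one arm inhales a study product three times a day and the other does not.

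If some RESP301 patients take a bronchodilator because of an airway reaction, the RESP301 users are a mixture of reactors and sicker patients. SOC users contain no such reactors; they have rescue for other reasons, such as the severity of COVID-19 or existing chronic lung disease. The two groups of users then differ in prognosis before any effect of RESP301 on progression. If reactions also depend on severity, the groups of non-users differ too.

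What is at stake is a supportive table. It would be presented as the impact of rescue on efficacy, while part or all of any difference between arms could come from who ended up in each row.

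**Working it through.** The SAP attaches no figure to this analysis, so there is nothing to reproduce. The check asks what the subgroup table would show if RESP301 had no effect at all.

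**Inputs from the SAP.** 300 patients randomised 2:1 (section 3.1), so 200 RESP301+SOC and 100 SOC. A 24% control event rate is one of three example rates in Appendix A. Rescue rates and their link to prognosis are not given. Everything else below is assumed.

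**Model 1: irritant use unrelated to severity.** Severity X is standard normal.

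- Event probability in both arms: p(X) = logistic(−1.5 + X), giving 22.1% overall.
- Severity-driven rescue: r(X) = logistic(−2.5 + X), giving 10.5% in SOC.
- In RESP301 a further fraction k takes rescue at random, so the probability of rescue is 1 − (1 − r)(1 − k).
- Event rate among users = E[p × P(rescue)] / E[P(rescue)]; for non-users, use 1 − P(rescue).

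Results by numerical integration:

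| k | Rescue use, SOC / RESP301 | Users, SOC vs RESP301 | False benefit in users | Non-users, SOC vs RESP301 |
|---|---|---|---|---|
| 10% | 10.5% / 19.5% | 35.9% vs 28.8% | 7.0 points | 20.5% vs 20.5% |
| 20% | 10.5% / 28.4% | 35.9% vs 26.2% | 9.7 points | 20.5% vs 20.5% |
| 30% | 10.5% / 37.4% | 35.9% vs 24.9% | 11.0 points | 20.5% vs 20.5% |

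Non-users show no bias because the factor (1 − k) does not depend on X and cancels.

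**Sampling noise at the planned size, k = 20%.** SOC users: 100 × 0.105 ≈ 11. RESP301 users: 200 × 0.284 ≈ 57. Standard error = √(0.359 × 0.641 / 10.5 + 0.262 × 0.738 / 56.9) = √0.0252 ≈ 0.16, or 16 points. The false benefit of 9.7 points is well inside one standard error.

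**Model 2: reactions related to frailty.** 30% of patients are frail with a 50% event risk. To give 24% overall in both arms, the robust risk is (0.24 − 0.30 × 0.50) / 0.70 = 12.9%. Rescue rates below are frail / robust.

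*Reactions more common in the frail: SOC 10% / 1%, RESP301 40% / 15%.*
- RESP301 users: (0.12 × 0.50 + 0.105 × 0.129) / 0.225 = 32.7%.
- SOC users: (0.03 × 0.50 + 0.007 × 0.129) / 0.037 = 43.0%. Risk ratio 0.76.
- Non-users: 21.5% RESP301 vs 23.3% SOC. Risk ratio 0.92.
- Both rows favour RESP301 although it does nothing.

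*Reactions mainly in the robust: SOC 10% / 2%, RESP301 10% / 30%.*
- Users: 17.5% vs 38.2%. Risk ratio 0.46.
- Non-users: 26.1% vs 23.3%. Risk ratio 1.12, a spurious harm.

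*Same rescue rates in both arms (10% / 2%).* The risk ratio is 1.00 in both rows. The distortion therefore requires rescue use to differ by arm.

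**The case against.** The strongest case on the other side is that nothing depends on this table. The efficacy analyses use all randomised patients as randomised. The primary test is a CMH analysis stratified by country and risk factors, and neither the interim rules nor the alpha allocation refers to rescue use. That stands, and it limits the point to a supportive analysis.

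The causal link is also inferred. The SAP does not say why rescue is given and nowhere ties it to nebulisation-related hyper-responsiveness. That stands too, so the point is that treatment may plausibly affect rescue use, not that it does.

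The sentence in section 4.7 could mean only a description of outcomes in users and non-users, without comparing arms. That is possible, and a by-use description of safety is reasonable for a nebulised product. But the wording promises an analysis of the impact on efficacy and excludes no arm comparison. The bar on formal analysis in section 4.9.1.6 follows a list that omits rescue use, so its reach is unclear. Leaving out a p-value would in any case not remove bias from the displayed rates.

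A reader might infer that the table is biased towards RESP301, in users and non-users alike. The documents do not support that: with severity-independent irritant use the non-users agree exactly, and with other rates a row can show harm. Nor would the artefact stand out in this trial, given about 11 SOC users under the assumed rates.

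**Conclusion.** The point holds in a limited form. Section 4.7 commits to an efficacy analysis by a post-randomisation variable that RESP301 nebulisation may affect. Arm contrasts among users, and under some assumptions among non-users, are then not randomised comparisons and can show spurious benefit or spurious harm.

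The size and direction cannot be determined from the SAP. The 7 to 11 points in users rest on the assumed severity model and on 10% to 30% irritant use in RESP301 only. The effects in non-users (risk ratios 0.92 and 1.12) appear only when reactions depend on frailty. At the planned size, such differences would be hard to tell from chance. The primary ITT analysis and the interim decisions are unaffected. This is a correction worth making to a supportive analysis, and it does not threaten the trial's main conclusion.

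**What to change.** Change section 4.7 as follows:

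- Delete the efficacy subgroup analysis by rescue use. If it is kept, restrict it to a descriptive display labelled as a non-randomised comparison from which no treatment effect is to be inferred.
- Keep the number and percentage of rescue users by arm, and report it as a tolerability result.
- State that efficacy is analysed by ITT regardless of rescue use. This matches section 4.5 and makes it explicit for rescue.

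A composite of progression or rescue should not be added as an efficacy analysis. In Model 1 at k = 20% it gives 28.9% in SOC and 1 − (1 − 0.289) × 0.80 = 43.1% in RESP301, an apparent harm of 14 points with no effect on progression. It would mix tolerability with efficacy and would depend on open-label decisions to give rescue.

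The cost is a small rewording of section 4.7 and possibly fewer tables. The descriptive efficacy split by rescue use is lost or carries a caveat.

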## 4.8 Treatment Compliance

Compliance with study treatment will be assessed via relative dose intensity (RDI). Relative dose intensity is defined as 100% times the actual dose intensity (ADI) divided by the intended dose intensity (IDI). Actual dose intensity for a patient is defined as the total dose received over all treatment days divided by the sum of the lengths of all treatment days. The intended dose intensity is the total dose assigned over all treatment days divided by the sum of the intended lengths of all treatment days. The assigned dose for **RESP301+SOC** is 6.0 mL per treatment administration taken three times a day for 10 days.

For example, the intended dose intensity (IDI) for RESP301 for a patient who completed 10 days of treatment three times a day would be:

$$6.0 \text{ mL} * 3 * 10 \text{ days} / 10 \text{ days} = 18.0 \text{ mL}$$

Summaries of ADI, IDI, and RDI will be presented for patients on the RESP301+SOC arm. The average number of dosing days will be presented as well.

A by-patient listing of study treatment compliance data will also be provided, containing the date of randomization, the date of last dose of study treatment, and the calculated RDI. A by-patient listing of exposure data will be provided.

## 4.9 Efficacy Evaluation

### 4.9.1 Analysis and Data Conventions

This study is designed to test for superiority. The null hypothesis for the treatment comparison will be that there is no difference in the rate of progression to at least one level higher of the modified WHO ordinal scale in RESP301 + SOC compared to SOC alone. The alternative hypothesis is that RESP301 +SOC reduces the rate of progression to at least one level higher in the modified WHO ordinal scale in COVID-19 at Day 14. Symbolically, this is expressed as follows:

$$\begin{aligned} H_0: p\text{WHO+1+RESP301+SOC} &\geq p\text{WHO+1+SOC} \\ H_a: p\text{WHO+1+RESP301+SOC} &< p\text{WHO+1+SOC} \end{aligned}$$

#### 4.9.1.1 Multi-center Studies

All centers will be pooled together in the efficacy analyses. If the results reveal impact of the centers, then ad hoc analyses will be performed. In that case, the centers may be grouped by geographic regions and evaluation of the consistency of treatment effects across geographic regions may be performed.

#### 4.9.1.2 Adjustments for Covariates

The primary efficacy analysis will be adjusted for the following baseline covariates:

CC1  
CC1  
CC1

CONFIDENTIAL

Project Document Version No. 2.0  
Project Document Effective Date: Date of last signature  
Page 17 of 31

1. Country
2. No risk factor (none of the criteria listed in [Section 3.1](#)), one risk factor (one single of the criteria in [Section 3.1](#)) or high-risk factor (2 or more of the criteria).

